8.2. Pharmacokinetic Analyses

8.2.1. Overview of Planned Pharmacokinetic Analyses

The pharmacokinetic (PK) analyses will be based on the Pharmacokinetic populations for Part 1 and Part 2, unless otherwise specified.

[Table 5](#) provides an overview of the planned analyses, with full details being presented in [Appendix 11: List of Data Displays](#).

Table 5 Overview of Planned Pharmacokinetic Analyses

Endpoints	Untransformed				Log-Transformed			
	Summary		Individual		Summary		Individual	
	F	T	F	L	F	T	F	L
Plasma GSK2586881 concentrations	Y ^{1,3}	Y	Y ^{1,2}	Y				
Pharmacokinetic Parameters		Y		Y		Y		

NOTES :

- T = Table, F = Figures, L = Listings, Y = Yes display generated.
- Summary = Represents TFL related to any summaries (descriptive statistics) of the observed raw data.
- Individual = Represents FL related to any displays of individual subject observed raw data.
- 1. Linear and Semi-Log plots will be created on the same display.
- 2. One output for one graph per subject and a further output with all subject profiles on the same graphic
- 3. Separate Mean (\pm SD) and Median plots will be generated.
- All tables and figures will be produced separately for the PK1 and PK2 populations. Listings will be produced for the overall PK population.

8.2.2. Drug Concentration Measures

Refer to [Appendix 3: Data Display Standards & Handling Conventions](#) (Section [10.3.3 Reporting Process & Standards](#)).

8.2.3. Pharmacokinetic Parameters

8.2.3.1. Deriving Pharmacokinetic Parameters

- Refer to [Appendix 3: Data Display Standards & Handling Conventions \(Section 10.3.3 Reporting Process & Standards\)](#).
- The pharmacokinetic parameters will be calculated by standard non-compartmental analysis according to current working practices and using Win Nonlin Pro V6.3 or greater.
- All calculations of non-compartmental parameters will be based on actual sampling times.
- Pharmacokinetic parameters described in [Table 6](#) will be determined from the plasma concentration-time data, as data permits.

Table 6 Derived Pharmacokinetic Parameters

Parameter	Parameter Description
AUC(0-2.5h) post-dose	Area under the concentration-time curve over the study period (pre-dose to 30 mins rest post chamber exit).
AUC(0.5-2.0h) post-dose	Area under the concentration-time curve over the time period for the hypoxia challenge (immediately prior to chamber entry to chamber exit).
AUC(0-∞)	Area under the concentration-time curve extrapolated to infinity.
Cmax	Maximum observed concentration, determined directly from the concentration-time data.
tmax	Time to reach Cmax, determined directly from the concentration-time data.
t½	Apparent terminal half-life will be calculated as: $t\frac{1}{2} = \ln 2 / \lambda_z$
CL	Clearance
V	Volume of distribution
Lambda_z	The first order rate constant associated with the terminal (log-linear) portion of the concentration-time curve.
Lambda_z_lower	First time point used in computing Lambda_z.
Lambda_z_upper	Last time point used in computing Lambda_z.
#pts	Number of points used in computing Lambda_z.
r-squared	R-squared of Lambda_z computation.

NOTES:

- Additional parameters may be included as required.
- Lambda_z is the terminal phase rate constant.

8.2.4. Population Pharmacokinetic (PopPK) Analyses

A population PK analysis may be conducted. The plasma concentration-time data may be merged with historical data and analysed as part of a population PK meta-analysis. The timeline for these analyses will be independent of the analysis described in this RAP. To support this analysis a NONMEM-specific data file will be generated, the specifications of which are provided in [Appendix 9: Population PK and Pharmacokinetic / Pharmacodynamic \(or Biomarker\) Analyses](#).

8.3. Pharmacodynamic and Biomarker Analyses

8.3.1. Overview of Planned Pharmacodynamic and Biomarker Analyses

The pharmacodynamic and biomarker analyses will be based on the Modified Intent-To-Treat populations (mITT, mITT1 and mITT2), unless otherwise specified. Biomarker data will be analysed for those subjects in the Modified Intent-To-Treat populations for whom a sample was obtained and analysed.

Table 7 provides an overview of the planned pharmacodynamic and Biomarker analyses, with full details of data displays being presented in [Appendix 11: List of Data Displays](#).

Table 7 Overview of Planned Pharmacodynamic and Biomarker Analyses

Endpoint	Absolute												Change from Baseline													
	Stats Analysis			Summary			Individual			Stats Analysis			Summary			Individual										
	T	F	L	T	F	F	L	T	F	L	T	F	F	L	T	F	F	L	T	F	F	L				
RAS Peptide Responses¹																										
Ang II				Y	Y	Y	Y	Y ¹	Y ¹																	
Ang(1-7)				Y	Y	Y	Y	Y ¹	Y ¹																	
Ang(1-5)				Y	Y	Y	Y	Y ¹	Y ¹																	
Other Biomarkers (Disease Biomarkers)																										
Surfactant Protein D				Y	Y	Y	Y	Y ¹	Y ¹																	
Ventilatory Parameters²																										
Oxygen consumption (VO ₂)				Y				Y																		
Carbon Dioxide Production (CO ₂)				Y					Y																	
Total Tidal Volume				Y					Y																	
Inspiratory Tidal Volume				Y					Y																	
Expiratory Tidal Volume				Y					Y																	
Total Respiratory Time				Y					Y																	
Inspiratory Time				Y					Y																	
Expiratory Time				Y					Y																	
Duty Cycle				Y					Y																	
Mean Respiratory Flow				Y					Y																	
Respiratory Rate				Y					Y																	
RAS Peptides vs PASP & Oxygen Saturation³																										
Ang II vs PASP					Y																					
Ang(1-7) vs PASP					Y																					
Ang(1-5) vs PASP					Y																					
Ang II vs Oxygen Saturation					Y																					
Ang(1-7) vs Oxygen Saturation					Y																					
Ang(1-5) vs Oxygen Saturation					Y																					

NOTES :

- T = Table, F = Figure, L = Listing, Y = Yes display generated.
- Stats Analysis = Represents TFL related to any formal statistical analyses (i.e. modelling) conducted.
- Summary = Represents TFL related to any summaries (descriptive statistics) of the observed raw data.
- Individual = Represents FL related to any displays of individual subject observed raw data.
- 1. Statistical analysis of RAS peptides and SPD to be performed for Part 2. Part 1 may also be analysed.
- 2. Parameters will be included in the same summary/figure/listing paging by RAS peptide where applicable
- 3. Scatter plots of x vs y for mITT population, panel by timepoint, include study part in a legend, one plot for PASP, one plot for Oxygen Saturation (page by RAS peptide).
- Unless otherwise stated as in #3, all tables and figures will be produced separately for the mITT1 and mITT2 populations. Listings will be produced based on the mITT population

8.3.2. Planned Pharmacodynamic and Biomarker Statistical Analyses

Planned Statistical Analyses
Endpoint(s)

 • RAS Peptide Responses: Ang II, Ang(1-7), Ang(1-5) • Disease Biomarker: Surfactant Protein D
Model Specification

 • Refer to Section 7.2. Change from baseline in PD/Biomarker endpoints will be analysed in a manner similar to the primary endpoint PASP. Data will be assessed prior to analysis to confirm the need for any data transformations. Log transformation highly likely to be required. • Analyses will be performed for Part 2. Part 1 may also be analysed. • Repeated measures timepoints of interest will be: 
 • Pre-dose (T0) • End of Infusion • 15 min Post-dose (T1) • 15-45 min Post-dose • 60 min post chamber entry (T2) • Immediately post exercise (T3) • Immediately post chamber exit • 30 mins post chamber exit (T4) 
 • Posterior probabilities of interest may include: • AngII: probability that the ratio <1, <0.50 and <0.25, representing any, 50% and 75% greater reduction in AngII levels on GSK2586881 compared to placebo • Ang(1-5) & Ang(1-7): probability that the ratio >1, >1.50 and >1.75, representing any, 50% and 75% greater increase in Ang(1-5) and Ang(1-7) levels on GSK2586881 compared to placebo • SPD: probability that the ratio <1, >1 and >1.5, representing any decrease, any increase and a 50% increase in SPD levels on GSK2586881 compared to placebo • Probability cut-offs may be re-assessed at the time of analysis
Model Checking

 • Refer to Appendix 8: Model Checking and Diagnostics for Statistical Analyses
Model Results Presentation

 • Summary tables for absolute by treatment and timepoint (as detailed above) (for Part 1 and

Planned Statistical Analyses

Part 2)
 
 • Listing of absolute data • Individual subject profiles by treatment group and timepoint (for Part 1 and 2) • Summary table of statistical analysis, adjusted change from baseline posterior medians and 95% credible intervals by treatment and timepoint, together with estimated posterior median treatment differences (GSK2586881 – Placebo) and 95% credible intervals for the change from baseline at ALL timepoints (not just T1 to T4), along with posterior probabilities of interest. (Part 2 and Part 1(as required)) • Figure of absolute data by timepoint (for Part 1 and 2) • Figure of statistical analysis adjusted change from baseline medians and 95% credible intervals by treatment group and timepoint (Part 2 and Part 1(as required))

8.4. Pharmacokinetic / Pharmacodynamic Analyses

The pharmacokinetic/pharmacodynamic (PK/PD) analyses will be based on the mITT and mITT2 population, unless otherwise specified. For the RAS peptides, PASP and Oxygen Saturation endpoints, exploratory plots vs pharmacokinetic concentrations will initially be reviewed to identify endpoints where there is a potential trend. If there is evidence for a trend, further PK/PD analyses may be conducted. The timeline for these analyses will be independent of the analysis described in this RAP. To support this analysis a NONMEM-specific data file will be generated, the specifications of which are provided in [Appendix 9: Population PK and Pharmacokinetic / Pharmacodynamic \(or Biomarker\) Analyses](#).

[Table 8](#) provides an overview of the planned PK/PD analyses with further details of data displays being presented in [Appendix 11: List of Data Displays](#). Details of missing data imputation specific to PK/PD graphics are provided in Section [10.5.2](#).

Table 8 Overview of Planned PK/PD Analyses

Endpoint	Absolute			
	Summary		Individual	
	T	F	F	L
RAS Peptide Ang II vs PK concentration		Y ¹		
RAS Peptide Ang(1-7) vs PK concentration		Y ¹		
RAS Peptide Ang(1-5) vs PK concentration		Y ¹		
PASP vs PK concentration		Y ²		
PASP (T2 & T3) vs AUC(0.5-2.0)		Y ²		

NOTES :

- Scatter plots, timepoints indicated by panel.
- 1. RAS peptides vs PK will form one graphic, page by RAS peptide. Study part will be identified by a different colour/symbol combination. To be produced for the mITT population.
- 2. Produced for Part 2 only (mITT2 population).
- T = Table, F = Figure, L = Listing, Y = Yes display generated.

10. APPENDICES

Section	Appendix
RAP Section 5 : General Considerations for Data Analyses & Data Handling Conventions	
Section 10.1	Appendix 1: Time and Events
Section 10.2	Appendix 2: Treatment States
Section 10.3	Appendix 3: Data Display Standards & Handling Conventions 
 • Study Treatment & Sub-group Display Descriptors • Baseline Definitions & Derivations • Reporting Process & Standards
Section 10.4	Appendix 4: Derived and Transformed Data 
 • General, Study Population & Safety • Pharmacodynamic and or Biomarkers
Section 10.5	Appendix 5: Premature Withdrawals & Handling of Missing Data 
 • Premature Withdrawals • Handling of Missing Data
Section 10.6	Appendix 6: Values of Potential Clinical Importance
Section 10.7	Appendix 7: Biomarker Details
Section 10.8	Appendix 8: Model Checking and Diagnostics for Statistical Analyses
Section 10.9	Appendix 9: Population PK and Pharmacokinetic / Pharmacodynamic (or Biomarker) Analyses
Other RAP Appendices	
Section 10.10	Appendix 10: Abbreviations & Trade Marks
Section 10.11	Appendix 11: List of Data Displays
Section 10.12	Appendix 12: Example Mock Shells for Data Displays

10.1. Appendix 1: Time & Events

10.1.1. Protocol Defined Time & Events

10.1.1.1. Screening and Follow up

Procedure	Screening ¹ (up to 28 days prior to Treatment Period 1, Day 1)	Follow up (7-10 days post last dose)	Notes
Informed consent	X		
Inclusion and exclusion criteria	X		
Demography	X		
Full physical exam, including height and weight	X	X	Height and weight to be measured at screening only. Weight at screening will be used for dosing calculation.
Alcohol, Drugs of Abuse, Smoking test	X		
Medical history (includes substance usage [and family history of premature CV disease])	X		Substances: Drugs, Alcohol, tobacco
Past and current medical conditions [including cardiovascular medical history]	X		
Serum OR urine pregnancy test (WCBP)	X		
HIV, Hep B and Hep C screen	X		
Laboratory assessments (include liver chemistries)	X	X	Non Fasting
Immunogenicity		X	
12-lead ECG	X	X	Tripplicate ECG required at screening.
Vital signs	X	X	Tripplicate vital signs required at screening.
Spirometry	X		
Echocardiogram	X		
Concomitant Medication review	X	X	
Hypoxia chamber plus exercise	X		Part 1: Tolerance to 4000m for 10 mins followed by incremental exercise testing to determine maximum oxygen uptake (VO2max) and calculate 70% of VO2max (to be used for the exercise challenge during the Treatment Periods). Part 2: Tolerance to 5000m for 10 mins followed by incremental exercise testing to determine maximum oxygen uptake (VO2max) and calculate 50% of

Procedure	Screening ¹ (up to 28 days prior to Treatment Period 1, Day 1)	Follow up (7-10 days post last dose)	Notes
Pharmacogenetic sample (PGx)	X		VO2max (to be used for the exercise challenge during the Treatment Periods) Can be taken any time after consent has been signed. Only required once and is optional.
AE/SAE review	X	X	As per timings detailed in protocol Section 7.2.1.1

1. Screening assessments are allowed to be conducted on more than one day

10.1.1.2. Treatment Period 1 and 2

Procedure	Treatment Period 1 and 2 (Washout 3-14 days)										Notes
	Times relative to start of dosing				Hypoxic Challenge ~80 min (Times relative to entry to Chamber)						
	Pre-dose	0h	15 min	15-45 min	0-60 min	60 min	60-70 min	Immediately after exercise	On exit from chamber	After 30 min rest	
Randomisation	X										Treatment Period 1 only. Randomisation can occur up to the day before the first treatment period
Brief physical exam	X										
Vital signs	X			X				X ⁵			X
Immunogenicity	X										
12-lead ECG	X			X							X
Echocardiogram	X		X		X		X ⁶ below		X		
Subject enters chamber					X						Subject enters chamber approximately 30 min after study treatment
Study Treatment (Dosing)		X									
Subject leaves chamber							X				Subject leaves chamber after the fourth echocardiogram, blood samples and vital signs have been taken.
Exercise challenge						X					Part 1: exercise at 70% VO ₂ max for ~5-10 min. Echo conducted immediately after. Part 2: exercise at 50% VO ₂ max for 2 min. Echo started at 2 min into the challenge, and the subject continues exercising.
Ventilatory parameters	X		X		X				X		Measurements to be taken 2 min before echocardiograms.

Procedure	Treatment Period 1 and 2 (Washout 3-14 days)										Notes
	Times relative to start of dosing				Hypoxic Challenge ~80 min (Times relative to entry to Chamber)						
	Pre-dose	0h	15 min	15-45 min	0-60 min	60 min	60-70 min	Immediately after exercise	On exit from chamber	After 30 min rest	
Pulse Oximetry (O2 saturation)	←-----→										Will be continuously monitored for safety. A measurement should be recorded at time of each echocardiogram and databased. Part 2: when the echo is recorded during the exercise challenge, pulse oximetry will be recorded immediately prior to initiation of the echo at 2 minutes into exercise.
Telemetry	←-----→										Will be continuously monitored for safety.
RAS Biomarkers	X	X ¹	X ²	X ³		X ²		X ²	X ⁴	X ²	
SP-D	X	X ¹	X ²	X ³		X ²		X ²	X ⁴	X ²	
PK sampling	X	X ¹	X ²	X ³		X ²		X ²	X ⁴	X ²	
AE/SAE review		←-----→									
Concomitant medication review	X										

1. Take at the end of the infusion
2. Taken immediately after echocardiogram
3. Immediately before entering the chamber
4. To be taken as soon as possible after leaving chamber
5. On this occasion ONLY, vital signs to be taken after the blood draw.
6. In Part 2, echo at this time-point taken 2 minutes into the exercise challenge (not immediately after exercise).

10.2. Appendix 2: Treatment States

10.2.1. Treatment States for AE Data

This study is a single dose two period crossover study. As such, AEs will be attributed to the treatment received within the relevant study period based on the dates and times of the AEs in relation to dosing date and time. This is as per IDSL dataset standards. This is detailed in the table below.

10.2.1.1. Treatment States for AE Dates

Treatment State	Definition
Pre-Treatment	
AE Start Date / Time < Study Treatment Start Date / Time (Period 1)
 
This will apply to all subjects enrolled into the study, including those not randomised. We may have non-randomised and randomised subjects who have pre-treatment AEs/SAEs. For non-randomised subjects these events will be captured in the 'non-randomised' listing. For randomised subjects these events will be captured in summary listings with treatment group='Pre-Treatment'.

On-Treatment (Period 1)	
If AE Start Date / Time is on or after Study Treatment Start Date / Time (Period 1) & before Study Treatment Start Date / Time (Period 2).
 
Study Treatment Start Date / Time (Period 1) ≤ AE Start Date / Time < Study Treatment Start Date / Time (Period 2)
 
For randomised subjects, this derivation ensures that AEs starting on or after the Period 1 dose up until the Period 2 dose will be captured and assigned to the Period 1 treatment.

On-Treatment (Period 2)	
If AE Start Date / Time is on or after Study Treatment Start Date / Time (Period 2) & before Follow-Up.
 
Study Treatment Start Date / Time (Period 2) ≤ AE Start Date / Time ≤ Follow-Up Date
 
For randomised subjects, this derivation ensures that AEs starting on or after the Period 2 dose up until the Follow-up Visit will be captured and assigned to the Period 2 treatment.

Post-Treatment	
If AE Start Date is on or after Follow-Up.
 
AE Start Date > Follow-Up Date
 
There shouldn't be any instances of this. Subjects will return for a follow-up and visit and any AEs would be documented at that point (and hence included in Period 2 treatment group). No further follow-up of patients is required.

Onset Time Since 1 st Dose (Days/Hours/Mins)	
If Study Treatment Start Date / Time (Period 1) ≤ AE Start Date / Time $= AE Start Date / Time - Study Treatment Start Date / Time (Period 1) + 1 \text{ (min)}$
 
Missing otherwise.
 
A calculation to assess the time since the Period 1 dose up until the start time of

Treatment State	Definition
	
the AE. This will be calculated for all AEs, regardless of which period/treatment the AE was assigned to.
 
Example:
 
If Period 1 Dose was administered at 08:00am 01OCT2016 and Period 1 AE started at 09:10am 01OCT2016, then onset time since first dose would be 0d 1h 11m.
 
If Period 2 Dose was administered at 08:30am 08OCT2016 and a Period 2 AE occurred on 08OCT2016 at 10:00am, then onset time since first dose would be 7d 2h 1m.

Onset Time Since Period Dose (Days/Hours/Mins)	
[PERIOD 1] If AE Start Date / Time is on or after Study Treatment Start Date / Time (Period 1) & before Study Treatment Start Date / Time (Period 2). = AE Start Date / Time – Study Treatment Start Date / Time (Period 1) +1 (min)
 
[PERIOD 2] If AE Start Date / Time is on or after Study Treatment Start Date / Time (Period 2) & on or before Follow-Up. = AE Start Date / Time – Study Treatment Start Date / Time (Period 2) + 1 (min)
 
Missing otherwise.
 
A calculation to assess the time since the dose in the relevant Period/treatment to which the AE is attributable to.
 
Example:
 
[PERIOD 1] If Period 1 Dose was administered at 08:00am 01OCT2016 and Period 1 AE started at 09:10am 01OCT2016, then onset time since period dose would be 0d 1h 11m (i.e. identical to value in previous row example in this case)
 
[PERIOD 2] If Period 2 Dose was administered at 08:30am 08OCT2016 and a Period 2 AE occurred on 08OCT2016 at 10:00am, then onset time since period dose would be 0d 1h 31m

Duration (Days/Hours/Mins)	
AE Resolution Date / Time – AE Start Date / Time + 1 (min)
 
Example:
 
AE started at 08:00am and resolved at 08:30am on the same day, then duration would be 0d 0h 31m

Drug-related	
If relationship is marked 'YES' on eCRF OR value is missing

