3.10.	miTT2	PFT3	Summary of Oxygen Saturation Change from Baseline (Part 2)	As above (Part 2 population)	SAC (GSK)
3.11.	miTT1	SAFE_T1 (non-standard)	Summary of Repeated Measures Bayesian Statistical Analysis of Change from Baseline in Oxygen Saturation (Part 1)	As per SAFE_T1 but parameter column could be removed. Note that adjusted treatment differences are included on page 2 of mock example. For OS expecting that we'll need to update the Posterior Probability labels, to <0%, <-3%, <-5%, where 5% is the clinical concern level for a treatment difference where GSK reduces OS to a greater extent. Please see Section 8.1.2 with regards to changes required should a log transformation be needed (SAFE_T2 applies in this case with addition of posterior probabilities to be added).	IA[1], SAC (GSK)
3.12.	miTT2	SAFE_T1 (non-standard)	Summary of Repeated Measures Bayesian Statistical Analysis of Change from Baseline in Oxygen Saturation (Part 2)	As above (Part 2 population)	SAC (GSK)
Pulmonary Vascular Resistance (PVR)					
3.13.	miTT2	PFT1	Summary of Pulmonary Vascular Resistance (PVR) (Part 2)	See comments for PASP	SAC (GSK)
3.14.	miTT2	PFT3	Summary of Pulmonary Vascular Resistance Change from Baseline (PVR) (Part 2)	See comments for PASP	SAC (GSK)
3.15.	miTT2	SAFE_T1 (non-standard)	Summary of Repeated Measures Bayesian Statistical Analysis of Change from Baseline in Pulmonary Vascular Resistance (PVR) (Part 2)	See comments for PASP. Note that adjusted treatment differences and posterior probabilities would initially be (<0, <0.1, <0.3)	SAC (GSK)

Safety : Tables					
No.	Population	IDSL / TST ID / Example Shell	Title	Programming Notes	Deliverable [Priority]
Adverse Events (AEs)					
3.16.	mITT1	AE1CP (same as CP_AE1x)	Summary of All Adverse Events by System Organ Class and Preferred Term (Part 1)	Summarise by treatment group. Any pre-treatment AEs to be included in the listing only. Will only be created for interim if sufficient number of AEs are observed.	IA[1] (GSK), SAC (FSP)
3.17.	mITT2	AE1CP (same as CP_AE1x)	Summary of All Adverse Events by System Organ Class and Preferred Term (Part 2)	As above (Part 2 population)	SAC (FSP)
3.18.	mITT1	AE1CP (same as CP_AE1x)	Summary All Drug-Related Adverse Events by System Organ Class and Preferred Term (Part 1)	Summarise by treatment group.	SAC
3.19.	mITT2	AE1CP (same as CP_AE1x)	Summary All Drug-Related Adverse Events by System Organ Class and Preferred Term (Part 2)	As above (Part 2 population)	SAC

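### SAP 10.2.1.1: for an adverse event that starts on the follow-up date, the wording says Post-Treatment while the formulas, explanation and onset rule say Period 2, so it could be left out of the by-treatment AE tables

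*SAP*

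**What the plan says.** Two adjacent rows of the table in SAP 10.2.1.1 set the boundary at follow-up, each in words and then as a formula.

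- **On-Treatment (Period 2), words:** "If AE Start Date / Time is on or after Study Treatment Start Date / Time (Period 2) & before Follow-Up".
- **On-Treatment (Period 2), formula:** "Study Treatment Start Date / Time (Period 2) ≤ AE Start Date / Time ≤ Follow-Up Date".
- **Post-Treatment, words:** "If AE Start Date is on or after Follow-Up".
- **Post-Treatment, formula:** "AE Start Date > Follow-Up Date".

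The text under the Post-Treatment formula says that no such events are expected, because subjects return for follow-up and "any AEs would be documented at that point (and hence included in Period 2 treatment group"). The row for onset time since the period dose, in the same table, takes Period 2 up to events "on or before Follow-Up".

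In 10.1.1.1, the row "Laboratory assessments (include liver chemistries") is marked at screening and at follow-up. The schedule for the treatment periods (10.1.1.2) has no laboratory row. For Table 3.16, section 10.11.5 instructs: "Summarise by treatment group. Any pre-treatment AEs to be included in the listing only". It does not mention Post-Treatment events.

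**The concern.** In both rows the words and the formula disagree about the follow-up day. A programmer who follows the words codes an event starting that day as Post-Treatment; one who follows the formulas codes it as Period 2. The by-treatment AE tables give Post-Treatment events no stated place, so the first choice could remove the event from both treatment columns.

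The day matters in this trial because follow-up is the only scheduled post-dose laboratory visit. The full physical examination is also repeated there, whereas the treatment periods have only a brief pre-dose one. Table 4 of the SAP plans laboratory listings but no laboratory summary table, so the AE tables are the only by-treatment summary in which an event arising from a follow-up laboratory result would be counted. Table 3.16 is assigned to the sponsor's team at the Part 1 interim and to a different team (FSP) for the final analysis, so two groups could read the same row differently.

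**Working it through.** The plan gives no figure to reproduce here. The check applies each rule to test events around the boundary.

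**Inputs.** Period 2 dose at 08:30 on 8 October 2016, taken from the worked example in 10.2.1.1. Follow-up on 16 October 2016, my choice: 8 days after the dose, inside the 7 to 10 day window in 10.1.1.1.

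**Rules.**
- *Words:* Period 2 if dose ≤ AE start and AE date < follow-up date; Post-Treatment if AE date ≥ follow-up date.
- *Formulas, date level:* Period 2 if dose ≤ AE start and AE date ≤ follow-up date; Post-Treatment if AE date > follow-up date.
- *Formulas, literal date/time:* Period 2 if dose ≤ AE date/time ≤ follow-up date at 00:00; Post-Treatment if AE date > follow-up date. The 00:00 is an assumption; the SAP does not state it.

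| AE start | Words | Formulas, date level | Formulas, date/time against 00:00 |
|---|---|---|---|
| 15 Oct, 10:00 | Period 2 | Period 2 | Period 2 |
| 16 Oct, 00:00 | Post-Treatment | Period 2 | Period 2 |
| 16 Oct, 10:00 | Post-Treatment | Period 2 | none |
| 17 Oct, 10:00 | Post-Treatment | Post-Treatment | Post-Treatment |

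The conflict is confined to the follow-up day. On that day the explanatory text and the onset-time row agree with the date-level formulas.

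**Size of one omitted event.** Section 3.1.1 gives 11 subjects randomised in Part 1, and 3.1.2 plans up to 14 in Part 2.
- Part 1: 1/11 = 9.1%.
- Part 2 at the planned maximum: 1/14 = 7.1%.

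One Part 1 subject did not complete both periods. If a treatment column therefore has 10 subjects, the figure is 1/10 = 10.0%. Each is an upper limit per event, because a subject with another event in the same row and treatment column is still counted.

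**The case against.** The strongest reply is that the SAP makes its intent clear. The Period 2 formula, the explanatory text and the onset-time row all put the follow-up day in Period 2, and only the two sentences of wording say otherwise. The plan also expects no Post-Treatment events, so one that appeared should be noticed. Nothing disappears from the report: Listing 13 covers all events in the mITT population, and Listing 14 covers serious ones. This stands. It makes silent loss less likely and shows which way to correct the text, but it does not remove the contradiction from a rule that has to be programmed.

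A reader might infer that the formulas themselves leave a follow-up-day event in no state. They do not. Compared as dates they are complementary, and the Post-Treatment formula, which sets a date against a date, points to that reading. The gap needs the midnight assumption. Because the Period 2 formula mixes a date/time with a date, it is a programming risk but not what the SAP states.

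A reader might also infer that every laboratory-detected event falls on the disputed day. The SAP does not say how such an event is dated. One found at follow-up but recorded with an earlier start keeps its period under every reading, and 10.3.3 allows for unscheduled visits.

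Finally, the table shell (AE1CP) is a company standard that is not shown, so the absence of a Post-Treatment column is inferred from the instruction to summarise by treatment group.

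**Conclusion.** The point holds as an internal inconsistency in an operative derivation rule. For an event starting on the follow-up date, the wording gives Post-Treatment and the rest of the table gives Period 2.

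Omission from Tables 3.16 to 3.21 is possible, not certain. It requires that the wording or the midnight comparison is programmed, that the recorded start date is the follow-up date, and that the tables show only the two treatments. Under those conditions a lost event can only lower the reported incidence, by at most 9.1 percentage points in Part 1 (10.0 with a denominator of 10) and 7.1 in Part 2 with 14 subjects; fewer subjects in Part 2 would raise the latter. The documents do not support saying that reported incidence will be too low. Adverse events are a secondary safety endpoint and the correction is nearly free, so it should be made before database freeze.

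**What to change.** In 10.2.1.1:

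- Change the end of the Period 2 wording to *on or before the Follow-Up Date*.
- Change the Post-Treatment wording to *after the Follow-Up Date*.
- State that the comparison with follow-up uses the date part of the AE start. The comparison with the Period 2 dose stays at date/time.

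This gives the date-level column of the table above: every event is in exactly one state, and the follow-up day is in Period 2, as the explanatory text intends.

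Align the Period 2 wording for concomitant medications in 10.2.2.1, which has the same mismatch. This is for consistency only: those data are listed, not tabulated.

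The cost is an edit to two SAP tables and a check of one line of derivation code. No new data are needed, and the design does not change.
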